10.1 Regulatory and ethical compliance

This clinical study was designed and shall be implemented and reported in accordance with the ICH Harmonized Tripartite Guidelines for Good Clinical Practice, with applicable local regulations (including European Directive 2001/20/EC, US CFR 21, and Japanese Ministry of Health, Labor, and Welfare), and with the ethical principles laid down in the Declaration of Helsinki.

10.2 Informed consent procedures

[REDACTED]

[REDACTED]

[REDACTED]

[REDACTED]

[REDACTED]

[REDACTED]

10.3 Responsibilities of the investigator and IRB/IEC

[REDACTED]

[REDACTED]

[REDACTED]

[REDACTED]

[REDACTED]

[REDACTED]

[REDACTED]

10.4 Publication of study protocol and results

[REDACTED]

[REDACTED]

11 Protocol adherence

[REDACTED]

[REDACTED]

[figure not shown]
[REDACTED]

[REDACTED]

[REDACTED]

*Calculated 25th percentile SBP values, based on data provided in the NHLBI (2004): The Fourth Report on the Diagnosis, Evaluation, and Treatment of High Blood Pressure in Children and Adolescents: National High Blood Pressure Program Working Group on High Blood Pressure in Children and Adolescents

** Estimate based on calculated 25th percentile SBP values for 1 yr + and AHA PALS Guidelines for the 5th percentile SBP ([Kleinman 2010](#))

[figure not shown]
16 Appendix 4: 5th Percentile Systolic Blood Pressure Table**Table 16-1 5th Percentile Systolic Blood Pressure Table (AHA PALS Guidelines)**

[figure not shown]
[figure not shown]
Age	SBP percentile	SBP (mmHg)
<1 month	5 th	60
<1 year	5 th	70
1 year	5 th	72
2 years	5 th	74
3 years	5 th	76
4 years	5 th	78
5 years	5 th	80
6 years	5 th	82
7 years	5 th	84
8 years	5 th	86
9 years	5 th	88
10 years	5 th	90
11 years	5 th	90
12 years	5 th	90
13 years	5 th	90
14 years	5 th	90
15 years	5 th	90
16 years	5 th	90

[figure not shown]
17 years	5 th	90
----------	-----------------	----

[figure not shown]
* AHA PALS guidelines 2010 ([Kleinman 2010](#)) are widely used criteria for hypotension in AHF patients. The formula (for 1 y/o and older: $70 \text{ mmHg} + 2 \times \text{Age}$, up to age 10) is understood to provide the 5th BP percentile up to 10 y/o. For children >10 y/o, the AHA PALS guidelines 2010 5th percentile is set at 90 mmHg. . NOTE: This formula approximates the population-based 5th percentile BP data; however, the margin of error increases with increasing age, with the PALS formula value generally providing a lower value.

19 Appendix 7: Oxygen delivery devices and FiO₂

Table 19-1 Oxygen delivery devices and FiO₂

Oxygen Device	FiO ₂ to be captured	Comment
Nasal Prongs/cannulas	1-2 l/min 25% 3-4 l/min 30% 5-6 l/min 35%	O ₂ delivery depends on the flow Indicated FiO ₂ is approximate, actual FiO ₂ depends on the patients breathing pattern and device positioning
Simple O ₂ mask	6-8 l/min 35% 8-10 l/min 45%	O ₂ delivery depends on the flow Indicated FiO ₂ is approximate, actual FiO ₂ depends on the patients breathing pattern and device positioning
Non-rebreathing mask	10-15 l/min 90%	O ₂ delivery depends on the flow Indicated FiO ₂ is approximate, actual FiO ₂ depends on the patients breathing pattern and device positioning
Venturi mask	24 – 50% depending on the connector used	Record what is indicated on the connector
Mask or helmet non-invasive ventilation	21-100%	Record ventilator reading
Invasive ventilation	21-100%	Record ventilator reading

Clinical Development

RLX030/Serelaxin

Study No. CRLX030A2208/ NCT02151383

Multicenter, open-label, dose escalation study to evaluate safety, tolerability and pharmacokinetics of RLX030 in addition to standard of care in pediatric patients from birth to <18 years of age, hospitalized with acute heart failure

Statistical Analysis Plan (SAP)

Addendum 1

Author: Trial Statistician, [REDACTED]
Document type: SAP Documentation
Document status: Final
Release date: 09-Aug-2018
Number of pages: 5

Property of Novartis
For business use only
May not be used, divulged, published or otherwise disclosed
without the consent of Novartis

Document History – Changes compared to previous final version of M3 (SAP) amendment 1

Date	Time point	Reason for update	Outcome for update	Section and title impacted (Current)
09-Aug-2018	Post DB lock	CSR addendum 1	Added additional analyses required for CSR addendum 1	NA

Table of contents

Table of contents	3
List of abbreviations	4
1 Introduction	5
2 Statistical methods	5
2.1 Analysis of the Pharmacokinetics (PK) data	5
2.2 Analysis of the secondary efficacy endpoints	5

List of abbreviations

CSR	Clinical Study Report
CV	Coefficient of variation
CVP	Central venous pressure
LAP	Left atrial pressure
PAP	Pulmonary artery pressure
PK	Pharmacokinetics
RAP	Report and Analysis Process
SAP	Statistical Analysis Plan

1 Introduction

This document provides details of the additional statistical analyses required to support the completion of the abbreviated Clinical Study Report (CSR) addendum 1 for the study CRLX030A2208.

2 Statistical methods

The following analyses will follow the general information and definitions outlined in the study statistical analysis plan CRLX030A2208 M3 amendment 1 (previous final version of SAP), including the definitions of baseline, analysis sets, age cohorts and dose groups.

2.1 Analysis of the Pharmacokinetics (PK) data

The PK concentration will be summarized descriptively by age cohort within each dose group as well as in the overall group, and time point, using n, mean, standard deviation, coefficient of variation (CV), geometric mean, geometric CV, median, minimum, and maximum.

The PK analysis set will be used for the above analysis. This analysis will include the PK concentration data at all scheduled PK sampling time points, i.e., at 0, 2, 16, 22, 32, 40, 48 hr. during the infusion, at 0.5, 4, 8 hours post infusion or study drug discontinuation, and on day 14/day 28.

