5.5.4 Instructions for prescribing and taking study treatment

The study drug infusion will begin after informed consent has been given in writing (ICF signed by parent/guardian and patient consent or assent where applicable) and the completion of all screening/baseline procedures, and will continue for a total 48 hours (16 hour infusion per dose level). The study drug should be administered via a peripheral or central iv line or port, as soon as possible, but no more than 5 hours after enrollment (i.e. confirmation of eligibility for the study and the baseline IRT contact where a medication number is assigned). Compatible filters and syringes which have been tested and qualified for use with serelaxin, must be used to prepare and administer the study drug. [REDACTED]

The required amount of study drug will be calculated for each patient for each dose titration level and will be withdrawn from the 6 mL vials (with 3.5 mL fill) contained in the study drug kits, added to a syringe of 5% dextrose solution (10% dextrose may also be considered), and then infused at a constant rate over a period of 16 hours for each titration level. [REDACTED]

Each dose level is infused over 16 hours. Dose escalation should only occur if

- the patient does not fulfill any requirement for dose adjustment or discontinuation (see [Section 5.5.5](#) Permitted dose adjustments of study treatment) on the preceding infusion rates, and
- the investigator considers dose escalation to be safe based on his global clinical assessment, including an evaluation of the patient's hemodynamic status (including physical examination ([Section 6.5.1](#)), vital signs and hemodynamic parameters, arterio-venous oxygen extraction) and a comparison of his/her current condition with the one before starting serelaxin and before the previous dose escalation.

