If the investigator considers it unsafe, based on his/her global clinical assessment, to increase the serelaxin dose to the next dose level the patient should remain on the same dose level for another 16 hours (if tolerated). At the end of this 16 hour period, another global clinical assessment must be done to determine whether or not it is safe to escalate the dose. If it is deemed safe at that time, the dose is increased to the next dose level in the sequence of the assigned dose group (i.e. low-dose or high-dose group), not the initially planned dose level, for the remainder of the 48 hour infusion time. For example, if a patient receives 3 μ g/kg/day for 16 hours and a decision is taken to that the patient should *not* be up-titrated to the next dose level, they are to be dosed at 3 μ g/kg/day for another 16 hours, if tolerated. If after the second 16 hours at 3 μ g/kg/day, a decision is taken to up-titrate the patient, they would then

[REDACTED]

receive a 10 μ g/kg/day, for 16 hours, again if tolerated. The total infusion time of serelaxin should not exceed 48 hours regardless of dose titration. All assessments, including PK sampling, should continue per protocol even if the dose rate is not escalated.

Study drug will be dispensed only by study staff qualified to perform that function under applicable local laws and regulations for the study site(s), according to the protocol and Assessment Schedule (see [Table 6-1](#)).

All dosages prescribed and dispensed to the patient and all dose changes during the study must be recorded on the Dosage Administration Record eCRF.

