5.5.5 Permitted dose adjustments of study treatment

This section describes the actions that are required if a systolic BP decrease (i.e. <5th percentile for age) occurs during the administration of study drug and is confirmed by two measurements taken 10 minutes apart (in patients with intermittent BP measurements) or by a consistent measurement over ≥ 5 min (in patients with invasive continuous BP measurements). This event is considered a “systolic blood pressure decrease event” (SBPDE) and must be recorded as such on the appropriate eCRF.

If the SBP falls to <5th percentile for the age of the patient ([AHA PALS guidelines 2010, Kleinman 2010](#), see [Appendix 4](#)) and is a confirmed SBPDE per the criteria in the previous paragraph, then the following steps are required:

1) In all patients:

Assess the patient and treat alternative causes of hypotension (consider hypovolemia, arrhythmia, heart-lung interactions, concomitant medications, pneumothorax or pericardial tamponade, hardware malfunction or measuring error etc.)

2) As clinically indicated, the following steps should be taken, preferentially in the indicated order (however, the options can be applied in sequence or separately at the investigator's discretion):

1. Increase the infusion rate of inotropic and/or vasoactive drugs as clinically indicated up to a vasoactive score of 20 and/or
2. Reduce the serelaxin infusion rate by 50% and/or
3. Discontinue serelaxin infusion

Patients who tolerate the reduced serelaxin infusion rate should remain on this reduced infusion rate for the remainder of the 48 hour infusion period, as tolerated. The exact time and date of the reduction of the study drug infusion rate must be recorded on the Drug Administration Record case report form. All assessments, including PK sampling, should continue per protocol even if the dose rate is reduced. Time from initiation of study drug infusion to completion must not exceed a total of 48 hours.

Dosing may be discontinued at any time at the discretion of the investigator. Reasons for which the investigator may discontinue the study drug include, but are not limited to, serious or intolerable AEs suspected to be causally related to study drug. In the event that study drug

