9.4.1 Variable(s)

Pharmacokinetic parameters will include C_{ss} (steady state concentration, estimated by C_{16hr} , C_{32hr} and C_{48hr} for each dose level), and CL (clearance, estimated using the following equation: $CL = \text{Rate of infusion}/C_{ss}$). Refer to [Section 6.6.2](#) for time points for pharmacokinetic (PK) assessments.

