5.4 Medical History

Medical history entered on the medical history CRF page at screening [REDACTED] will be coded using the MedDRA dictionary. Medical history and protocol solicited events (only for post-surgical patients) will be listed at the individual patient level for the SAF.

6 Study medication

Data entered on the Dosage Administration Record CRF page will be listed at the individual patient level for the SAF. This will include dose prescribed (ug/kg/day), start/end date and time of the infusion, concentration (ug/ml), rate of infusion (mL/h) and reason for the dosage administered.

7 Concomitant medication

Prior and concomitant medications, continuous intravenous concomitant medications, surgical and medical procedures and use of mechanical ventilator will be listed at the individual patient level for the SAF. The medication name will be coded using therapeutic class (ATC code) and preferred term (PT).

8 Pharmacokinetic (PK) data

PK concentration data will be listed at the individual patient level for the SAF. Invalid PK concentration data will be noted. A graphical presentation will be employed to show individual serelaxin concentration-time (actual) profiles by age cohort within each dose group. These figures will be prepared for the PK analysis set.

9 Selected vital signs for safety (SBP, DBP, HR and RR)

Summary statistics (n, mean, standard deviation, median, Q1, Q3, minimum, and maximum) will be provided by age cohort within each dose group for the measurement at each visit and change from baseline values for the following parameters for the safety population:

- Systolic blood pressure (SBP)
- Diastolic blood pressure (DBP)
- Heart rate (HR)
- Respiratory rate (RR)

10 Adverse Events (AEs), SAEs and Deaths

A treatment emergent adverse event is defined as an adverse event that occurs at or after the start of the study treatment. Treatment emergent adverse events including non-serious AEs, SAEs, AEs (including non-serious AEs and SAEs) and AEs leading to discontinuation will be

summarized descriptively (using number and percentage) by age cohort within each treatment group and in the overall group. Similarly, deaths will be summarized descriptively as appropriate. The number and percentage of these events will be presented by system organ class (SOC) and MedDRA preferred term (PT). All AEs will be listed at the individual patient level. These analyses will be performed for the SAF.

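### Addendum 1 averages PK concentrations by planned dose group and scheduled time, and no visible rule separates samples taken at a held or reduced infusion rate (minor, cheap to improve)

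*SAP*

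**What the plan says.** Addendum 1, section 2.1, has one PK variable, concentration, and these strata: "The PK concentration will be summarized descriptively by age cohort within each dose group as well as in the overall group, and time point". The times are the scheduled ones and include 16, 32 and 48 h. Section 2 of the Addendum takes its dose groups and analysis sets from SAP Module 3 Amendment 1, whose Introduction defines the two dose groups by their full three-step sequences.

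Protocol 5.5.4 sets the plan: "Each dose level is infused over 16 hours". If the investigator considers escalation unsafe, the patient may stay on the same level for a further 16 hours and then move to the next level in sequence, so every later level is also delayed. For sampling: "All assessments, including PK sampling, should continue per protocol even if the dose rate is not escalated". Protocol 5.5.5 lists a 50% reduction among the responses to a confirmed fall in systolic pressure, again with sampling continued: "Patients who tolerate the reduced serelaxin infusion rate should remain on this reduced infusion rate for the remainder of the 48 hour infusion period". If the infusion is stopped, sampling moves to the post-infusion schedule.

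Amendment 1, section 6, covers dosing: "Data entered on the Dosage Administration Record CRF page will be listed at the individual patient level for the SAF". Its section 8 lists the concentrations and adds a figure: "A graphical presentation will be employed to show individual serelaxin concentration-time (actual) profiles by age cohort within each dose group". Its Introduction says that PK parameters will not be provided because the study ended early. Protocol 9.4.1 and 9.4.2 had planned Css and CL (infusion rate divided by Css), by age cohort and by dose within dose group.

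**The concern.** For a patient who escalates as planned, time within dose group identifies the dose level, and the Addendum table is right. For a patient who was held or reduced, it does not: the 32 or 48 h sample, or any later sample after a reduction, stays in the same cell but comes from a lower rate. The 16 h value cannot be affected by a hold, because the first escalation decision falls at 16 h. Only a reduction during step 1 can lower it.

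Holds and reductions are permitted actions, not protocol deviations, so neither the deviation clause of the PK set nor Table 2-1 of Amendment 1 removes them. Analysis by treatment received does not help, since the only treatments defined are the two sequences.

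The effect of age on PK is a primary objective (Protocol 2.1), and this is the only numerical PK summary in the SAP documents. An off-rate sample lowers one age cohort's geometric mean for a dosing reason, and the table would not show that reason.

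**Working it through.** **Inputs.** Planned cell sizes (Protocol 3.1): 3 in every low-dose cell; in the high-dose group, 3 (maximum 6) in cohorts 1 and 2, and 6 in cohorts 3 and 4. Coefficient of variation 30% (Protocol 9.7). Dose levels and the 50% reduction are from Protocol 5.5.4 and 5.5.5. Assumptions: concentration proportional to rate, steady state at sampling, and exactly one off-rate patient in the cell.

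**The plan's own precision figures.** Limits = exp(±t(0.975, n−1) · s · √[χ²(0.80, n−1)/(n−1)] / √n), with s = 0.30 on the log scale.
- n = 6: 68.4% to 146.2% (stated 68% to 146%).
- n = 3: 38.9% to 257.4% (stated 39% to 257%).

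Both reproduce, so s = 0.30 is used below.

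**Shift in the cell geometric mean.** With one of n patients at a fraction r of the planned rate, the factor is r^(1/n).

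| Event | Infused v planned (µg/kg/day) | r | n = 3 | n = 6 |
|---|---|---|---|---|
| One hold | 3 v 10 (low, 32 h); 30 v 100 (high, 48 h) | 0.30 | 0.67 | 0.82 |
| One hold | 10 v 30 (low, 48 h; high, 32 h) | 0.33 | 0.69 | 0.83 |
| Halved within the current step | any | 0.50 | 0.79 | 0.89 |
| Halved in step 2, kept to 48 h | 5 v 30 (low) | 0.17 | 0.55 | 0.74 |
| Halved in step 2, kept to 48 h | 15 v 100 (high) | 0.15 | 0.53 | 0.73 |
| Halved in step 1, kept to 48 h | 1.5 v 30 (low); 5 v 100 (high) | 0.05 | 0.37 | 0.61 |

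Cells of six are planned only in the high-dose group, so the 0.74 in the fourth row is arithmetic without a planned low-dose cell behind it. A single hold at 16 h affects both the 32 h and the 48 h cell.

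Against the planned ranges, every factor in the table lies inside except the last row: 0.37 is below 0.39, and 0.61 is below 0.68.

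**Would a reader notice?** Geometric CV = √(exp(s² + (ln r)²/n) − 1).
- Clean cell: √(exp(0.09) − 1) = 31%.
- r = 0.30: 88% (n = 3) or 63% (n = 6).
- r = 0.50: 53% or 43%.

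The 95th centile of the geometric CV in a clean cell is 56% (n = 3) or 47% (n = 6). In a simulation of 400,000 cells, that centile was exceeded in 84% or 82% of cells at r = 0.30, but in only 38% or 32% at r = 0.50. A hold usually shows as an odd CV; a half rate often does not.

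In units of the standard error that a reader would see, the shift is (|ln r|/n) / √[(s² + (ln r)²/n)/n]. This is 0.92 or 0.85 at r = 0.30, and 0.80 or 0.69 at r = 0.50.

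**The overall group.** The Addendum does not say whether this combines dose groups. If it does, the 16 h cell mixes 3 and 10 µg/kg/day. Its log variance is s² + (ln(10/3))² · n₁n₂/[N(N−1)], which gives a geometric CV of 83% (3 + 3 patients) or 76% (3 + 6) with no off-plan dosing at all.

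**The case against.** The strongest reply is that this table supplements an abbreviated report of a study that stopped early. Amendment 1 says openly that the full analyses might not be meaningful and that PK parameters would be left out. The listings give each patient's prescribed dose, infusion times, rate and reason for the dosage, together with every concentration; the individual profiles use actual time. In cells of three, a reader could find the cause and work out CL by hand. The rules for noting a concentration as invalid are not shown, so off-rate samples might be flagged. No off-rate patient is documented, and the cells of six were due to open last and may be empty.

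Most of this stands and sets the weight of the point. What it leaves untouched is that listings let a reader reconstruct the cause but do not correct the table.

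Stronger readings that a reader might infer are not supported:
- *A commitment was broken.* Omitting CL was declared, the protocol does not specify the actual rate in its CL formula, and it only permits pooling across dose groups.
- *The table will produce a false age effect.* For a single hold or a halving within the current step, the shift is less than one visible standard error and lies inside the planned precision. Nothing says how off-rate samples fall across cohorts.
- *Stopped infusions distort the cells.* Sampling then moves to the post-infusion schedule, so the value is absent, not distorted.
- *CL repairs everything.* Rate divided by concentration equals CL only at steady state. After a reduction in mid-step that depends on the time since the change, and the visible text gives no half-life.

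**Conclusion.** The point holds as a minor one. The table's strata follow the planned sequence, permitted dosing can depart from it with sampling continued, and no visible rule separates the samples concerned. The illustrated effect on a cell geometric mean runs from a factor of 0.89 (half rate in the current step, six patients) to 0.37 (halved in step 1 and kept to 48 h, three patients); a single hold gives 0.67 to 0.83. These sizes rest on dose-proportional concentrations, steady state, log-SD 0.30, planned cell sizes and one off-rate patient per cell. If a reduced rate has not yet reached steady state, the shift is smaller. Whether any cell was affected cannot be told from the documents. The permitted holds and reductions are taken as given and are not judged here.

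**What to change.** In Addendum 1, section 2.1:
1. Summarize the 16, 32 and 48 h concentrations by age cohort and the dose level actually being infused at sampling, with off-plan samples shown separately or footnoted.
2. List, per patient, CL = actual infusion rate / concentration (rates are per kg, so CL is per kg), with the time since the last rate change.
3. Give n, geometric mean CL and geometric CV by age cohort, only for samples judged at steady state.
4. Define the overall group. If it combines dose groups, give no infusion-period concentration summary for it.

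The cost is one derived variable, one listing and one table. No new data are needed, since rates, times and concentrations are already listed under Amendment 1, sections 6 and 8. The drawbacks are a small descriptive addition after database lock, imprecise or empty cells, and a cell of three that may fall to two on-plan patients.

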Secondary Objective	Secondary objective To evaluate the hemodynamic effects of different doses of serelaxin given as an iv infusion in addition to standard of care in hospitalized pediatric patients with AHF (efficacy parameters: arterial blood pressure,), left atrial pressure (LAP), pulmonary artery pressure (PAP – systolic and diastolic) central venous and arterial oxygen saturation, urine output, and blood lactate levels)
Study design	This is a multicenter, open-label, dose-escalation study to evaluate the safety, tolerability and pharmacokinetics of RLX030 in addition to standard of care in pediatric patients from birth to <18 years. A fixed dose titration scheme will be used for this study. A total duration of 48 hours is planned for the constant iv serelaxin infusion with dose escalations every 16 hours. A low-dose group and a high-dose group will be enrolled sequentially in every age cohort. During this 48-hour treatment period, the serelaxin dose rates to be administered are 3 µg/kg/day, 10 µg/kg/day and 30 µg/kg/day in the low-dose group; 10 µg/kg/day, 30 µg/kg/day and 100 µg/kg/day in the high-dose group. These dose rates are anticipated to be safe in the pediatric population and are based on the dose range investigated in adults with AHF.

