9.4.2 Statistical model, hypothesis, and method of analysis

The PK parameters C_{ss} and CL will be mainly summarized descriptively by age cohort and dose within each dose group. A graphical presentation will be employed to show mean and individual RLX030 concentration-time profiles for each age cohort and each dose group.

The PK parameters C_{ss} and CL may be pooled across dose group (high/low-dose) within each age cohort and summarized as appropriate by dose level and age cohort for 10 $\mu\text{g}/\text{kg}/\text{day}$ and 30 $\mu\text{g}/\text{kg}/\text{day}$, respectively.

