9.4.4 Supportive analyses

9.5 Analysis of secondary variables

9.5.1 Efficacy variables

Hemodynamic parameters (secondary)

Secondary endpoints will be assessed at baseline, prior to each dose escalation, and at 24 hr post end of infusion. Secondary endpoints will include an assessment of hemodynamic effects on routinely measured hemodynamic parameters as listed below:

- arterial BP
- central venous pressure (CVP)
- left atrial pressure (LAP) and pulmonary artery pressure (PAP – systolic and diastolic), if available
- central venous and arterial oxygen saturation
- urine output
- blood lactate levels

For arterial BP, CVP, LAP, PAP, central venous and arterial oxygen saturation, urine output and blood lactate levels, the absolute values at baseline and each time point (when these parameters are measured), as well as the change from baseline will be descriptively summarized by age cohort and dose group and for all patients.

[REDACTED]

[REDACTED]

[REDACTED]

[REDACTED]

[REDACTED]

[REDACTED]

[REDACTED]

[REDACTED]

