2.2 Analysis of the secondary efficacy endpoints

Summary statistics (n, mean, standard deviation, median, the first quartile (Q1), the third quartile (Q3), minimum, and maximum) will be provided by age cohort within each dose group as well as in the overall group for the measurement at each visit and change from baseline values for the following secondary efficacy variables:

- Central venous pressure (CVP)
- Left atrial pressure (LAP)
- Pulmonary artery pressure (PAP- systolic and diastolic)
- Central venous and arterial oxygen saturation
- Urine output
- Blood lactate levels (arterial and central venous lactate)

The safety set will be used for the above analyses. Data collected at the following assessment time points/visits will be included in the analyses: at baseline, prior to each dose escalation, at 48 hours post infusion start, and at 24 hours post end of infusion.

Clinical Development

RLX030/Serelaxin

Study No. CRLX030A2208 / NCT02151383

Multicenter, open-label, dose escalation study to evaluate safety, tolerability and pharmacokinetics of RLX030 in addition to standard of care in pediatric patients from birth to <18 years of age, hospitalized with acute heart failure

Module 3 – Detailed Statistical Methodology

Amendment 1

Author(s):  Trial Statistician

Document type: RAP Documentation Amendment

Document status: Final

Release date: 29-Jun-2017

[figure not shown]
Number of pages:

Property of Novartis
Confidential
May not be used, divulged, published or otherwise disclosed
without the consent of Novartis

Table of contents

Table of contents	3
List of tables	4
List of abbreviations	5
	
1 Introduction	6
2 Analysis sets	7
3 Subgroup definitions	9
4 Baseline and post baseline definitions	9
5 Subject Disposition, background and demographic characteristics	10
5.1 Subject disposition	10
5.2 Protocol deviations	10
5.3 Background and demographic characteristics	10
5.4 Medical History	11
6 Study medication	11
7 Concomitant medication	11
8 Pharmacokinetic (PK) data	11
9 Selected vital signs for safety (SBP, DBP, HR and RR)	11
10 Adverse Events (AEs), SAEs and Deaths	11
11 Other data	12
12 Interim analyses	13
13 Sample size and power considerations	13
14 Appendix 1 - Reference	13

List of tables

Table 2-1	Rules for subject classification in the analysis sets based on protocol deviations and non-protocol deviation classification criteria	8
Table 3-1	Specification of subgroups.....	9

List of abbreviations

AE	Adverse Event
BP	Blood Pressure

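### SAP Addendum 1's undefined overall-group PK summary pools planned doses 3.0- to 3.33-fold apart at each on-infusion time, so its mean and CV belong to no dose

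*SAP*

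**What the plan says.** **PK.** SAP Addendum 1, section 2.1: "The PK concentration will be summarized descriptively by age cohort within each dose group as well as in the overall group, and time point". The on-infusion samples are "at 0, 2, 16, 22, 32, 40, 48 hr. during the infusion", followed by samples at 0.5, 4 and 8 h after infusion and later visits.

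**Haemodynamics.** Section 2.2 of the Addendum uses the same layout, "by age cohort within each dose group as well as in the overall group for the measurement at each visit". Protocol 9.5.1 already had an all-patient summary: the variables "will be descriptively summarized by age cohort and dose group and for all patients".

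**Dose steps.** The planned rates are "3 µg/kg/day, 10 µg/kg/day and 30 µg/kg/day in the low-dose group" and 10, 30 and 100 µg/kg/day in the high-dose group, stepping every 16 hours in both (Protocol synopsis and 3.1).

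**Pooling in the protocol.** Section 9.4.2 says that Css and CL "may be pooled across dose group (high/low-dose) within each age cohort and summarized as appropriate by dose level and age cohort", naming 10 and 30 µg/kg/day.

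**What else is reported on PK.** The SAP (Module 3 Amendment 1), section 1, drops the PK parameters because the study stopped early. Its section 8 lists concentrations and plots individual profiles. The Addendum table is therefore the only place where PK summary statistics appear.

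**The concern.** A concentration summary is useful only if the reader knows which dose it describes. Pooling both dose groups by scheduled time averages patients on planned rates about three-fold apart. The resulting mean or geometric mean corresponds to neither rate. The CV mixes differences between patients with a difference fixed by design, and a reader could take it for paediatric PK variability.

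The effect of age on PK is a primary objective, and Css and CL by dose level are no longer reported. The concentration table thus carries more weight than it would in a full report. For haemodynamics, the secondary objective concerns the effects of different doses, which a column mixing doses cannot address.

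**Working it through.** **1. What the overall group means.** No document defines it. The SAP describes the count of patients in each analysis set twice: section 2 gives a total for all patients, and section 5.1 gives the total in the overall group. The likeliest meaning is therefore all patients, both dose groups together. Two other readings are possible: each age cohort pooled over dose, or all ages inside one dose group. The last of these mixes no doses.

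**2. Planned rates at the same clock time (µg/kg/day).**

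| Samples | Low | High | High/low |
|---|---|---|---|
| 2, 16 h | 3 | 10 | 3.33 |
| 22, 32 h | 10 | 30 | 3.00 |
| 40, 48 h | 30 | 100 | 3.33 |

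Post-infusion samples follow final rates of 30 and 100. Time 0 is not mixed by dose.

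**3. The plan's variability figure.** Protocol 9.7 and SAP section 13 assume a 30% CV for Css and give 80%-assurance ranges for the 95% CI. The formula exp(±t(0.975, n−1) · σ · √[χ²(0.80, n−1)/((n−1)n)]) with σ = 0.30 returns (68.4%, 146.2%) for n = 6 and (38.9%, 257.4%) for n = 3. These match the stated (68%, 146%) and (39%, 257%), so 30% is the plan's within-dose spread.

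**4. Pooled geometric CV at the steady-state times.** Assume Css proportional to dose, equal clearance at all ages and full escalation. Let f be the high-dose share and r the dose ratio. Then

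pooled log-variance = ln(1.09) + f(1−f)·(ln r)², and geometric CV = √(exp(variance) − 1).

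The planned minimum is 3 × 4 = 12 low-dose and 3 + 3 + 6 + 6 = 18 high-dose patients, so f = 18/30 = 0.6 and f(1−f) = 0.24.

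- 16 and 48 h, r = 3.33: 0.086 + 0.24 × 1.450 = 0.434; geometric CV 74%.
- 32 h, r = 3: 0.086 + 0.24 × 1.207 = 0.376; geometric CV 68%.

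The dose gap supplies 0.348/0.434 = 80% and 0.290/0.376 = 77% of the pooled log-variance. Using the plan's σ² = 0.09 instead of ln(1.09) leaves 74% and 68% unchanged. By mix:

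| Low:high | 16, 48 h | 32 h |
|---|---|---|
| 3:3 | 75% | 69% |
| 3:6 | 71% | 65% |

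These treat the mix as a proportion; an n−1 divisor would raise them somewhat.

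**5. Age contrast, only if the overall group is also split by age cohort.** The pooled geometric mean rate is low^(1−f) · high^f.

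- 16 h: 5.48 at 3:3 and 6.69 at 3:6, ratio 1.22. The ratio is the same at 48 h.
- 32 h: 17.3 and 20.8, ratio 1.20.
- If cohorts 1 and 2 enrol their maximum of six high-dose patients, every cohort is 3:6 and the ratio is 1.00.
- If one cohort had low-dose patients only (an assumption; the documents do not give actual enrolment), the ratio to it would be 1.73 to 1.83 for a 3:3 cohort and 2.08 to 2.23 for a 3:6 cohort.

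**6. After the change.** With dose groups kept apart, or pooled only at the same infused dose, r = 1. Under the same assumptions the geometric CV returns to 30% and any false age ratio to 1.00.

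**The case against.** The overall summary is an extra descriptive column. Both Addendum sections keep the summaries for each age cohort inside its dose group, and SAP section 8 adds individual profiles in the same layout. No test, model or decision uses the total. If only one dose group was enrolled, nothing is mixed. All of this stands, and it limits how serious the point is.

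Three stronger readings are tempting, and the documents do not support them.

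- A reader might infer that the plan creates a false age difference. That needs the overall group to be split by age cohort and the low:high mix to differ between cohorts. The likelier reading is a single all-patient group, which contains no age contrast. The direction is not fixed either: high-dose patients in the youngest cohorts enrol last, so early stopping could leave them with fewer high-dose patients than planned, the reverse of the design.
- A reader might infer that the Addendum overrides a protocol rule. Protocol 9.4.2 is permissive and concerns Css and CL. Those were dropped by the SAP amendment, not by the Addendum, which adds concentration summaries.
- A reader might infer that the Addendum introduces a bias into haemodynamics. The all-patient column was already in Protocol 9.5.1, and a bias would need a dose-response that the documents do not establish. The one relevant statement, on adult hypotension events (Protocol 3.6), reports none.

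The objection does not rescue the pooled PK figures themselves. SAP section 9 already leaves out an overall group for time-course vital signs, so omitting it would fit the sponsor's own practice.

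**Conclusion.** The point holds for PK. On the natural reading, Addendum 2.1 produces concentration means and CVs that belong to no dose at every on-infusion time after time 0, with planned rates 3.0- to 3.33-fold apart. That ratio comes straight from the dose schedule.

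The CV of about 74% or 68%, against the plan's 30%, rests on dose-proportional PK, equal clearance, full escalation and planned enrolment; across 3:3 and 3:6 mixes it is 65 to 75%. A false age ratio is conditional: 1.20 to 1.22 at 3:3 versus 3:6 if the overall group is split by age, 1.00 if the mixes are equal, and of unknown size and direction after early termination.

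For haemodynamics only the narrower statement holds: a post-baseline all-patient column cannot be read as the effect of any one dose. Because unmixed rows remain, this should be corrected but does not undermine the main layout.

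**What to change.** - **Addendum 2.1:** for concentrations after the start of infusion, replace the overall group with all ages within each dose group.
- **Any pooling across dose groups:** do it by the dose level actually being infused (10 or 30 µg/kg/day, in line with Protocol 9.4.2) or on dose-normalised concentrations. Do not assign dose by clock time, since Protocol 5.5.4 and 5.5.5 allow a dose level to be held or the rate to be halved.
- **Addendum 2.2:** for post-baseline haemodynamics, use all ages within each dose group, or keep the all-patient column and label it as mixing doses. Do not pool haemodynamic change by dose level across different clock times. That would mix times since baseline and prior serelaxin exposure.
- **Unchanged:** the summaries for each age cohort inside its dose group stay as the main analysis.

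The cost is a wording change and a re-run of descriptive tables, with no new data. One total column is lost.
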